5.3 Screen Failures

Screen failures are defined as subjects who consent to participate in the clinical study but are not subsequently randomized. A minimal set of screen failure information is required to ensure transparent reporting of screen failure subjects to meet the Consolidated Standards of Reporting Trials (CONSORT) publishing requirements and to respond to queries from regulatory authorities. Minimal information includes demography, screen failure details, eligibility criteria, and any SAE unrelated to the disease under investigation.

Individuals who do not meet the criteria for participation in this study (screen failure) may be rescreened. Rescreened subjects should be assigned the same subject number as for the initial screening.

6. STUDY TREATMENTS

Study treatment is defined as any investigational product(s) (including marketed product comparator and placebo) or medical device(s) intended to be administered to a study subject according to the study protocol. Study treatment in this study refers to acalabrutinib.

6.1 Treatments Administered

6.1.1 Dosing and Duration of Treatment

Acalabrutinib treatment should be administered within 6 hours of randomization on Day 1.

Subjects will take acalabrutinib 100 mg capsules by mouth bid for 10 days (a maximum of 20 doses). Capsules will be taken with water. The capsules should be swallowed intact and subjects should not attempt to open capsules or dissolve them in water. For subjects requiring a proton-pump inhibitor (PPI), acalabrutinib must be administered as described in Section 6.1.3.1.

Acalabrutinib can be taken with or without food.

Retreatment with acalabrutinib is not allowed.

BSC will be administered in both arms per Investigator's discretion and institutional guidelines.

6.1.2 Missed Dosing Windows and Doses

The bid doses should be scheduled approximately 12 hours apart. It is recommended that acalabrutinib be taken as close to the scheduled time as possible (within ± 1 hour). However, if the scheduled time is missed, it can be taken up to 3 hours after the scheduled time, with a return to the normal schedule upon the following dose for 10 days (a maximum of 20 doses).

If the 3-hour dosing window is missed, the dose must be skipped on that day. Study drug may be held for a maximum of 3 consecutive days (6 consecutive doses) from expected dose due to toxicity. If a dose is missed due to an adverse event (AE) or for any other reason, missed doses should be completed so the subject receives a maximum of 20 doses of study drug, even if this is beyond the 10-day dosing period.

6.1.3 Special Considerations

6.1.3.1 Drug-drug Interactions

Drug-drug interactions may occur with some of the drugs being used as BSC (eg, drugs that are moderate inhibitor of CYP3A, gastric acid reducing agents), and dosing of acalabrutinib may need to be adjusted. Please refer to Section 6.5.4 for detailed information and guidance.

Subjects on concomitant PPIs must take acalabrutinib with at least 100 mL of COCA-COLA[®] at room temperature. Other cola beverages (eg, Diet Coke[®], COCA-COLA Zero Sugar) or juices are not permitted. The capsules should be swallowed intact and subjects should not attempt to open capsules or dissolve them in COCA-COLA. **NOTE:** COCA-COLA contains glucose (5 g per 100 mL). Blood glucose levels of diabetic subjects must be monitored as clinically indicated and blood glucose-lowering medications adjusted accordingly.

Administration of acalabrutinib with COCA-COLA mitigates the effect of PPIs. Several acidic beverages with pH similar to COCA-COLA were assessed (eg, orange drink, lemonade, COCA-COLA Zero Sugar, cranberry juice, and grapefruit juice) but not found to be optimal. In healthy subjects, pharmacokinetic (PK) exposure following 100-mg acalabrutinib suspension in COCA-COLA (nasogastric delivery) is similar in the presence or absence of PPIs, and comparable to that of the 100-mg acalabrutinib capsule. In addition, based on a verified physiologically-based biopharmaceutics model (Pepin et al 2019), acalabrutinib exposure is predicted to be similar between the administration of 100-mg acalabrutinib capsule with 100 mL COCA-COLA in the presence of PPIs and the 100-mg acalabrutinib capsule taken with water. Overall, these data support the use of acalabrutinib in subjects who need to take PPIs for the management of various acid-related disorders.

6.1.3.2 Subjects With Respiratory Failure and Who Can Still Swallow Pills

Subjects who have respiratory failure before completing the maximum of 20 doses and who are still able to swallow pills, will be permitted to continue treatment with acalabrutinib for the maximum of 20 doses, according to the Investigator's clinical judgment.

6.1.3.3 Subjects No Longer Able to Swallow Pills

Subjects who can no longer swallow pills will not be eligible to continue acalabrutinib treatment.

6.1.3.4 Vomiting After Acalabrutinib Treatment

If vomiting occurs after taking acalabrutinib, the subject should not retake acalabrutinib until the next scheduled dose.

6.1.3.5 Discharged From Hospital Before Treatment Completion

Subjects who are discharged from the hospital before they have completed 10 days (20 doses) of acalabrutinib therapy will be required to complete the remaining dosing at home. They should adhere to their established dosing schedule and treatment guidelines, including in cases where subjects remain on PPIs. These subjects must complete a drug dosing diary to be faxed or mailed back to the study site.

6.2 Acalabrutinib Preparation/Handling/Storage/Accountability

Acalabrutinib should be stored according to the instructions on the label affixed to the package of the drug product.

If a drug shipment arrives damaged or if there are any other drug complaints, a Product Complaint Form should be completed and emailed to the Sponsor or the Sponsor's representative. Refer to the pharmacy manual and the Investigator's Brochure for additional information regarding the drug product to be used in this study.

The Investigator or designee (eg, pharmacist) must confirm appropriate temperature conditions have been maintained during transit for all study treatment received and any discrepancies are reported and resolved before use of the study treatment.

Only subjects enrolled in the study may receive study treatment and only authorized site staff may supply or administer study treatment. All study treatments must be stored in a secure, environmentally controlled, and monitored (manual or automated) area in accordance with the labeled storage conditions with access limited to the Investigator and authorized site staff.

The Investigator, institution, or the head of the medical institution (where applicable) is responsible for study treatment accountability, reconciliation, and record maintenance (ie, receipt, reconciliation, and final disposition records).

Further guidance and information for the final disposition of unused study treatment are provided in the Clinical Study Agreement.

6.3 Measures to Minimise Bias: Randomisation and Blinding

Given the urgent nature of the COVID-19 pandemic, this will be an open-label study. However, the study is randomized and include stratification factors as outlined in Section 4.1.

6.3.1 Subject Enrollment and Randomization

All eligible subjects will be centrally randomized using an interactive response technology (IRT) that will assign the subjects to either acalabrutinib plus BSC versus BSC, stratified by the stratification factors defined in Section 4.1. Before the study is initiated, log-in information and directions for the IRT will be provided to each site.

Investigators should keep a record (ie, the subject screening log) of subjects who entered screening.

At screening, the Investigators or suitably trained delegate will:

- Obtain informed consent before any study specific procedures are performed.
- Obtain a unique 7-digit enrollment number (E-code), through the IRT the following format (ECCNNXXX: CC being the country code, NN being the center number, and XXX being the subject enrollment code at the center). This number is the subject's unique identifier and is used to identify the subject on the electronic case report forms (eCRFs).
- Determine subject eligibility (see Section 5.1 and Section 5.2).

At randomization, once the subject is confirmed to be eligible, the Investigator or suitably trained delegate will:

- Log the E-code and stratification factors (age [≥ 65 vs < 65 years] and comorbidities [present vs absent]) in the IRT system and the system will sequentially randomize the eligible subject to 1 of the 2 treatment arms.
- If the subject is ineligible and not randomized, the IRT should be contacted to terminate the subject in the system.
- Subjects will begin treatment on Day 1. Treatment should start no more than 6 hours after being randomized. Subjects must not be randomized and treated unless all eligibility criteria have been met.

If a subject withdraws from participation in the study, then his/her enrollment/randomization code cannot be reused. A withdrawn subject will not be replaced.

6.3.1.1 Procedures for Handling Incorrectly Enrolled or Randomized Subjects

Subjects who fail to meet the eligibility criteria should not, under any circumstances, be enrolled or receive study medication. There can be no exceptions to this rule. Subjects who are enrolled, but subsequently found not to meet all the eligibility criteria must not be randomized or initiated on treatment and must be withdrawn from the study.

Where a subject does not meet all the eligibility criteria but is randomized in error, or incorrectly started on treatment, the Investigator should inform the study physician immediately, and a discussion should occur between the study physician and the Investigator

regarding whether to continue or discontinue the subject from treatment. The study physician must ensure all decisions are appropriately documented and that the potential benefit:risk profile remains positive for the subject.

6.3.1.2 Methods for Assigning Treatment Groups

The actual treatment assigned to subjects will be determined by the randomization scheme in the IRT. A stratified permuted block randomization scheme will be used, with the stratification factors defined in Section 4.1. The randomization scheme will be produced by a computer software program that incorporates a standard procedure for generating randomization numbers.

Randomization codes will be assigned strictly sequentially, within each stratum, as subjects become eligible for randomization.

6.3.1.3 Methods for Ensuring Blinding

This is an open-label study for the personnel at study sites. Specific treatment to be taken by a subject will be assigned using an IRT. The site will contact the IRT prior to the start of study treatment administration for each subject. The site will record the treatment assignment on the applicable case report form, if required. To maintain the integrity of the study, the Sponsor's personnel directly involved in the study conduct will, under no circumstances, view data aggregated by treatment arm during the course of the study.

6.4 Treatment Compliance

The study treatment should only be used as directed in this protocol. Details of treatment with the study treatment, including change from the dosing schedule, dose interruptions, dose reductions, and dose discontinuations, should be recorded in the eCRF. The investigational product will not be distributed to the study site until the contract is concluded between the study site and the Sponsor. The Investigator or designee is responsible for managing the investigational product from time of receipt by the study site until the destruction of all unused investigational product at that site. The Investigator(s) is responsible for ensuring that all unused investigational product is returned to the site by the subject(s).

6.5 Concomitant Therapy

6.5.1 Premedications

No specific premedications or supporting medications are required in conjunction with acalabrutinib administration.

6.5.2 Permitted Concomitant Therapy

BSC for COVID-19 is required for all subjects in this study except as listed in Section 5.2 and Section 6.5.3. Given the rapid emergence of new data related to COVID-19, BSC could

change during the duration of the study. The use of therapies such as remdesivir, therapeutic plasma, corticosteroids, or other immunomodulatory agents (eg, tocilizumab) is permitted if recommended by local authorities and part of institutional policies or guidelines. The concomitant administration of immunosuppressive agents with acalabrutinib may require additional safety monitoring as determined by the treating clinician. Investigators should maintain prohibitions of certain concurrent medications for other reasons as listed in Section 6.5.3.

6.5.3 Prohibited or Restricted Concomitant Therapy

The medications listed below are prohibited for all randomized subjects.

Medications Prohibited for All Subjects in Both Treatment Arms Through Day 28

Immunomodulatory drugs, intended as treatment for COVID-19 but not considered standard of care according to local institutional guidelines, are prohibited for all randomized subjects in the study through Day 28. Subjects who are taking immunomodulatory drugs for other medical conditions (eg, tocilizumab for rheumatoid arthritis) may continue with treatment upon discussion with the Medical Monitor.

Medications Prohibited for All Subjects in Both Treatment Arms Through Day 10

Strong CYP3A inhibitors or inducers: Drug-drug interactions may occur with some of the drugs being used as BSC (eg, drugs that are strong inducers or strong inhibitors of CYP3A). The concomitant use of strong inhibitors of CYP3A (see Appendix E) should be avoided by all subjects on the study. If a subject requires a strong CYP3A inhibitor while on treatment with acalabrutinib, discontinue acalabrutinib treatment. Conversely, concomitant administration of a strong inducer of CYP3A has the potential to decrease exposure of acalabrutinib and could reduce efficacy. Therefore, the concomitant use of strong CYP3A inducers should be avoided by all subjects in the study. If a subject requires a strong CYP3A inducer while on treatment with acalabrutinib, discontinue acalabrutinib. For additional information on drugs with potential drug-drug interactions, refer to Section 6.5.4.

Certain anticoagulants: Warfarin or equivalent vitamin K antagonists (eg, phenprocoumon) are prohibited for all subjects in the study. Subjects who require prophylaxis or therapeutic anticoagulation for thrombosis (deep vein thrombosis or pulmonary embolism) will be allowed to receive therapeutic anticoagulation with a non-vitamin K inhibitor class of anticoagulants (eg, heparin or low-molecular-weight heparin).

Refer to Section 5.2 for additional restrictions on concomitant therapy.

6.5.4 Acalabrutinib Drug-drug Interaction Guidance in the Presence of Life-threatening COVID-19 Infection

Drug-drug interaction recommendations provided for acalabrutinib in this protocol are made with respect to the presence of life-threatening COVID-19 infection and ability to achieve pharmacodynamic (PD) Btk receptor occupancy steady-state in target B-cell and monocytic populations. Therefore, the Sponsor recommends that all eligible subjects with COVID-19 begin dosing with acalabrutinib 100 mg bid. The duration of acalabrutinib therapy will be limited to 10 days (a maximum of 20 doses). Table 4 provides moderate CYP3A inhibitors and acid reducing agent guidance for subjects with COVID-19. Refer to Appendix E for a list of common CYP3A inhibitors/inducers and gastric acid reducing medicines.

Table 4	Acalabrutinib Use with Moderate CYP3A Inhibitors and Gastric Acid
	Reducing Agents

	Co-administered Medicines	Recommended Acalabrutinib Use
CYP3A Inhibitor	Moderate CYP3A inhibitor	Monitor subjects closely for adverse reactions if taking moderate CYP3A inhibitors. For subjects who experience an intolerable adverse event (ie, Grade 3-4) attributed to acalabrutinib therapy, reduce the dose to 100 mg once daily.
Gastric Acid Reducing Medicines	Proton-pump inhibitors (PPIs)	Avoid concomitant use. If PPI concomitant use cannot be avoided, dose modification of acalabrutinib is not necessary; however, acalabrutinib must be administered with at least 100 mL of COCA-COLA to improve acalabrutinib absorption (refer to Section 6.1.3.1). Other cola beverages are not permitted.
	H2-receptor antagonists	Take acalabrutinib 2 hours before taking a H2-receptor antagonist.
	Antacids	Separate dosing by at least 2 hours.

6.5.4.1 Active Substances That May Increase Acalabrutinib Plasma Concentrations CYP3A Inhibitors

Co-administration with a strong CYP3A inhibitor (200 mg itraconazole qd for 5 days) increased acalabrutinib maximum observed concentration (C_{max}) and area under the concentration-time curve (AUC) by 3.7- and 5.1-fold in healthy subjects (N=17), respectively.

Consider alternative therapies that do not strongly inhibit CYP3A activity. In subjects requiring strong CYP3A inhibitors (eg, ketoconazole, conivaptan, clarithromycin, indinavir, itraconazole, ritonavir, telaprevir, posaconazole, voriconazole), discontinue acalabrutinib treatment.

6.5.4.2 Active Substances That May Decrease Acalabrutinib Plasma Concentrations CYP3A Inducers

Co-administration of a strong CYP3A inducer (600 mg rifampin qd for 9 days) decreased acalabrutinib C_{max} and AUC by 68% and 77% in healthy subjects (N=24), respectively.

Consider alternative therapies to strong inducers of CYP3A activity (eg, phenytoin, rifampin, carbamazepine). Avoid St. John's wort which may unpredictably decrease acalabrutinib plasma concentrations. If these inducers cannot be avoided, discontinue acalabrutinib treatment.

Gastric Acid Reducing Medications

Acalabrutinib solubility decreases with increasing pH. Co-administration of acalabrutinib with an antacid (1 g calcium carbonate) decreased acalabrutinib AUC by 53% in healthy subjects. Co-administration with a PPI (40 mg omeprazole for 5 days), decreased acalabrutinib AUC by 43%.

If treatment with an acid reducing agent is required, consider using an antacid (eg, calcium carbonate), or an H2-receptor antagonist (eg, famotidine). For use with antacids, separate dosing by at least 2 hours. For H2-receptor antagonists, take acalabrutinib 2 hours before taking the H2-receptor antagonist.

Due to the long-lasting effect of PPIs, separation of doses with PPIs may not eliminate the interaction with acalabrutinib. In subjects requiring treatment with PPIs (eg, omeprazole, esomeprazole, lansoprazole, dexlansoprazole, rabeprazole, or pantoprazole) during the study, acalabrutinib must be administered with at least 100 mL COCA-COLA at room temperature to improve acalabrutinib absorption (see Section 6.1.3.1). Other cola beverages are not permitted.

Dose modification of acalabrutinib is not necessary when co-administered with gastric acid reducing medications.

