- 12. Uncontrolled or untreated symptomatic arrhythmias, myocardial infarction within the last 6 weeks, or congestive heart failure (NYHA Grade 3 or 4).

Exception: Subjects with controlled, asymptomatic atrial fibrillation during screening are allowed to enroll on study.

13. History of chronic hypercarbia, respiratory failure in past 6 months, or use of home oxygen in the setting of severe chronic respiratory disease.

- 14. Quadriplegia.
- 15. History of primary immunodeficiency, tuberculosis, progressive multifocal leukoencephalopathy (PML), aspergillus or other invasive mold/fungal infection, or received organ or bone marrow transplantation within 6 months of randomization.
- 16. Serology status reflecting active hepatitis B or C infection.
 - a) Subjects who are hepatitis B core antibody (anti-HBc) positive and who are hepatitis B surface antigen (HBsAg) negative will need to have a negative or undetectable hepatitis B viral load by quantitative polymerase chain reaction (PCR) result before randomization. Those who are HBsAg positive or have detectable hepatitis B viral load by PCR will be excluded.
 - b) Subjects who are hepatitis C virus (HCV) antibody positive will need to have a negative PCR result before randomization. Those who are hepatitis C PCR positive will be excluded.
- 17. Known active HIV with detectable viral load or CD4 counts < 500 cells/mm³.

Prior/Concomitant Therapy

- 18. Treatment with a strong cytochrome P450 (CYP)3A inhibitor (within 7 days before first dose of study drug) or inducer (within 14 days before first dose of study drug).
- Subjects are excluded who have already received prior immunomodulatory/ immunosuppressive treatment intended as specific treatment for COVID-19 (after randomization these agents may be permitted – see Section 6.5.2). Note: Steroids are permitted prior to randomization and on study..
- 20. Active participation in other drug clinical trials or received treatment with an investigational drug within 5 half-lives or 30 days (whichever is longer) of randomization/enrollment.

Exception: Subjects may receive COVID-19-specific antiviral drugs (eg, remdesivir, hydroxychloroquine).

- 21. Requires or is receiving specific anticoagulation with warfarin or equivalent vitamin K antagonists (eg, phenprocoumon) within 7 days prior to randomization. Other anticoagulants are permitted.

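### The vitamin K antagonist ban ends at Day 10, but acalabrutinib dosing can run past Day 10 and no rule says to stop acalabrutinib if such a drug is then required

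*Protocol*

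**What the plan says.** Protocol 6.5.3 sorts its banned drugs under timed headings. The anticoagulant paragraph sits under "Medications Prohibited for All Subjects in Both Treatment Arms Through Day 10", next to the paragraph on strong CYP3A inhibitors and inducers. Its ban reads "Warfarin or equivalent vitamin K antagonists (eg, phenprocoumon) are prohibited for all subjects in the study" and has no end day of its own, so the heading sets the period. The same paragraph lets a subject who needs prophylactic or therapeutic anticoagulation have a non-vitamin K agent, with heparin and low-molecular-weight heparin as examples.

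The acalabrutinib course is defined by a dose count as well as by days. Protocol 6.1.1 sets twice-daily dosing for 10 days, at most 20 doses. Protocol 6.1.2 adds: "If a dose is missed due to an adverse event (AE) or for any other reason, missed doses should be completed", up to the same total of 20. Sections 6.1.2 and 6.7 both accept that this may take dosing beyond the 10-day period, and both cap a toxicity hold at 3 consecutive days (6 doses). SAP 3.2.2 describes two adherent schedules. The one with an evening first dose ends on the morning of Day 11.

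For the other drug class under the Day 10 heading, 6.5.3 says "If a subject requires a strong CYP3A inhibitor while on treatment with acalabrutinib, discontinue acalabrutinib treatment". Strong inducers have a matching instruction, and 6.5.4.1 and 6.5.4.2 repeat both. For VKAs there is no counterpart in 5.2, 6.5.3, 6.5.4, 6.6.1, the 6.7 table, 7.1 or Appendix E. Section 7.1 refers the site back to 6.5.3.

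**The concern.** The sponsor singled out VKAs: exclusion criterion 21 bars them at entry and then says "Other anticoagulants are permitted". Protocol 6.6.1 reports bleeding events on acalabrutinib, some of them fatal. A ban adopted on that footing should cover every day on which acalabrutinib is taken. As written, it is tied to a calendar day that dosing can pass.

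For strong CYP3A drugs the same calendar limit does little harm, because their stop instruction applies for as long as the subject is on treatment. VKAs have no such backstop. A site that follows the heading could start warfarin from Day 11 while doses remain. Some of those doses may be taken at home, since 6.1.3.5 requires discharged subjects to finish the course there.

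Extended dosing can also fall on subjects with a recent low platelet count. The 6.7 table allows acalabrutinib to restart after a Grade 4 platelet decrease that recovers to Grade 2 or better within 3 days, and the held doses are then made up.

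**Working it through.** **Inputs**
- 20 doses, 12 hours apart (Protocol 6.1.1 and 6.1.2; SAP 3.2.2).
- First dose on Day 1, morning or evening. Dosing should begin within 6 hours of randomization (Protocol 6.3.1), so the hour of randomization largely decides which.
- Missed doses are made up at the end of the course (Protocol 6.1.2 and 6.7).
- One toxicity hold is at most 6 consecutive doses (same sections).
- The VKA ban ends with Day 10 (Protocol 6.5.3 heading).

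**Formula.** Number the 12-hour slots from Day 1 AM = 1, so slot s falls on day s/2 rounded up; odd slots are AM and even slots PM. Let k be the number of doses missed within Days 1 to 10 and made up later.
- Morning start: last dose in slot 20 + k. Slots 1 to 20 lie within Day 10, so k doses fall after it.
- Evening start: last dose in slot 21 + k. Slots 2 to 20 (19 slots) lie within Day 10, so k + 1 doses fall after it.

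**The plan's own figure.** Evening start with k = 0 gives slot 21, which is Day 11 AM. This agrees with SAP 3.2.2.

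**Results**

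| Start | Missed and made up (k) | Last slot | Last dose | Doses after Day 10 | Share of 20 |
|---|---|---|---|---|---|
| Morning | 0 | 20 | Day 10 PM | 0 | 0% |
| Evening | 0 | 21 | Day 11 AM | 1 | 5% |
| Morning | 1 | 21 | Day 11 AM | 1 | 5% |
| Evening | 1 | 22 | Day 11 PM | 2 | 10% |
| Morning | 6 (one maximal hold) | 26 | Day 13 PM | 6 | 30% |
| Evening | 6 (one maximal hold) | 27 | Day 14 AM | 7 | 35% |

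The only schedule in the table that ends inside the ban is a morning start with nothing missed. The overlap arises even with perfect adherence, in the evening-start schedule that the SAP itself describes.

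**Stop rules side by side.** Under the Day 10 heading, strong CYP3A inhibitors and inducers are to be avoided, with an order to discontinue acalabrutinib if one is required on treatment. VKAs are prohibited and a substitute is named, but nothing is said about acalabrutinib if a VKA is required. After Day 10 the CYP3A instruction still applies to a subject who is dosing. The VKA prohibition does not.

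**The case against.** **The existing safeguards make this rare.** For harm to arise, a subject must pass exclusion criterion 21, develop a new need for anticoagulation, be given a VKA although heparin is allowed, and have this happen between Day 11 and the last dose. An adherent subject has at most one dose in that interval. Grade 3 or 4, serious or intracranial bleeding means discontinuation under 6.7, so those subjects generate no make-up doses. Section 7.1 allows the Investigator to stop treatment, and Protocol 8 sends immediate safety concerns to the Medical Monitor. All of this stands and keeps the point small. It does not close the gap: the exclusion acts only at entry, the bleeding rule acts only after a bleed, and a site following the heading has no prompt to call the Medical Monitor.

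**The named substitute partly explains the missing stop rule.** While the ban applies, a subject who needs anticoagulation is directed to heparin, so requiring a VKA is a narrow residual case. This also stands. The missing instruction matters mainly for doses after Day 10.

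**Stronger readings that the documents do not support**
- A reader might infer that the end of the ban is ambiguous. The VKA sentence gives no end day, whereas the immunomodulator sentence states that those drugs "are prohibited for all randomized subjects in the study through Day 28". But the CYP3A paragraph under the same Day 10 heading also refers to all subjects in the study and gives no end day. The phrase describes the subjects, and the heading sets the period.
- A reader might infer that a third of the course typically goes uncovered. The 30% and 35% figures need a full 6-dose hold that is then completely made up.
- A reader of Appendix I might infer that a VKA stop rule was dropped by mistake, because the Amendment 2 entry mentions one. That entry describes superseded text and is no evidence of an error.

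**Conclusion.** The point holds as a minor safety correction. Followed as written, 6.5.3 lets the VKA ban lapse while acalabrutinib doses remain, and no current sentence requires acalabrutinib to stop if a VKA is then required. The uncovered tail is 1 dose for an adherent evening start and up to 6 or 7 doses after one maximal hold.

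These counts assume 12-hour slots, all misses within Days 1 to 10, and full make-up. The limit on holds is for consecutive doses, so repeated holds could extend dosing further.

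The number of subjects affected cannot be calculated. The documents give no split of morning and evening starts, no rate of missed doses and no rate of new VKA use. Given exclusion criterion 21 and the heparin route, few of the roughly 30 Arm 1 subjects are likely to be involved. The documents also do not quantify the added bleeding risk of a VKA over heparin, so no excess event rate can be claimed. Power, error rates and the primary analysis are unaffected.

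**What to change.** Make two edits to Protocol 6.5.3.

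1. Add a stop instruction to the anticoagulant paragraph, parallel to the CYP3A one: a subject who comes to require a VKA before finishing acalabrutinib must discontinue acalabrutinib.
2. Reword the heading, or move the anticoagulant paragraph out from under it, so that in Arm 1 the VKA ban runs through Day 10 or the last acalabrutinib dose, whichever is later. Arm 2 stays at Day 10, because those subjects take no acalabrutinib and a longer ban would bring them no stated safety benefit.

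A later fixed day, such as Day 14, should not be written into the paragraph while the Day 10 heading stands above it. The two would contradict each other, and Arm 2 would be restricted for 4 more days.

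The cost is a few lines of text, with no change to visits, data collection, sample size or analysis. Arm 1 subjects still dosing would face a longer VKA restriction: to Day 11 AM for an adherent evening start, and to Day 13 PM or Day 14 AM after one maximal hold. Heparin and low-molecular-weight heparin stay available throughout. The arms would differ in this restriction only for those subjects and those days. SAP 1.3 records recruitment as complete with 62 randomized, so for any subject who has finished dosing the change corrects the text only.
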